#### Before Surgery

https://ecap.hss.edu/eCAP/ResourceAdministration/Project/PrintSmartForms?Project=com.webridge.entity.Entity%5BOID%5B7 E7099039664F74FA0FE0FE... 11/36

Pre-op (Holding Area)

# PACU, 1 hour after admission PACU, 2 hours after admission PACU, ready for

# POD 1 discharge

Identify eligible patients on schedule day before surgery. Confirm length of surgery.

RA X

Obtain consent

Anes MD/ Surgeon

X

Assess readiness for PACU Discharge (q15

RA X (if not met) X (if not met) X (if not met)

1/18/2017 Print: 2016-0499 - Spinal versus General Anesthesia with Popliteal and Adductor Canal Blocks for Ambulatory Foot and Ankle Surgery. A Double-Blinded... ID: 2016-0499 min until criteria Section: met) PART II - Clinical Research Proposal - Interventions or Observations NRS pain, PONV, PQRS Cognitive RA Domain XXX (if not ready for discharge) ХХ Backache/TNS Headache/PDPH and RA X X Collect opioid and non-opioid consumption 2.0 Will you be collecting human fluid or tissue? Yes No If yes, what will you be collecting? Fluid Tissue (Intraoperative and/or outpatient collection) Help Help Data Collection 1.0 Indicate what data will be collected. Variable Time point(s) Data Source Who Collects? Demographics: DOB, MRN, Race, Ethnicity, BMI, Gender, Phone number https://ecap.hss.edu/eCAP/ResourceAdministration/Project/PrintSmartForms?Project=com.webridge.entity.Entity%5BOID%5B7 E7099039664F74FA0FE0FE... 12/36 RA X X (for PACU duration) X ORSDS RAXX Leiden Perioperative care Patient Satisfaction questionnaire (LPPSq) RA X Leiden Discomfort and Needs RA X X X (if not ready for discharge) XXBlock assessment RA X X (when spinal wears off or (Baseline awakened from reading) GA)

Blinding Assessment RA X

Pre-op Medical Record Research Assistant Comorbidities, Risk factors associated with outcomes Pre-op Medical Record Research Assistant

ID: 2016-0499 Randomization/Group Section: PART assignment II - Clinical Pre-op Research Proposal - Interventions Randomization or Observations scheme

Research Assistant created by staff member not involved in project

ASA, Type of anesthesia, induction time, anesthesia start & end time, difficult spinal/general, TQ time

https://ecap.hss.edu/eCAP/ResourceAdministration/Project/PrintSmartForms?Project=com.webridge.entity.Entity%5BOID%5B7 E7099039664F74FA0FE0FE... 13/36

Intra-op Anesthesia Record Research Assistant

Type of surgery, surgery start & end time

Intra-op Medical Record Research Assistant

Time from PACU admission to readiness for PACU discharge

Patient: Aldrete score (Aldrete JA. The post- anesthesia recovery score revisited. J Clin PACU, every 15 minutes

Anesth 1995) and after anesthesia end time

Postanesthesia

Research Assistant

Discharge Scoring System (Marshall and Chung. Curr Opin Anesthesiol 1997)

Opioid consumption Pre-op, PACU, POD 1

Medical Patient

Record and

Research Assistant

Opioid-related side effects PACU (2 hours), POD 1

Patient: ORSDS ([name] et al. A&A 2011)

Non-opioid analgesic medications Pre-op, PACU, POD 1

Medical Patient

Record and

Research Assistant

Pain at rest and with movement (at the time of questioning)

Pre-op, PACU (1 hour and 2 hours), POD 1

Patient: NRS (0-10) Research Assistant

Nausea and vomiting

Pre-op, PACU (1 hour Patient: and 2 hours), POD 1

Incidence (yes/no) and severity

Research Assistant (NRS)

Postoperative Quality Recovery Scale (PQRS) Cognitive Domain

Pre-op, PACU (1 hour and 2 hours), POD 1

Patient: PQRS Research Assistant

Satisfaction with perioperative care

Patient: Leiden Perioperative care Patient Satisfaction questionnaire

POD 1

(LPPSq). questionnaire Full

(Caljouw,

Research Assistant

Beuzekom, Boer. BJA 2008). Willingness to get same treatment again

Postoperative discomfort and needs

Patient: Leiden Perioperative care Patient

Pre-op, PACU (1 hour and 2 hours) and POD 1

Satisfaction questionnaire (LPPSq) (Caljouw,

Research Assistant

ID: 2016-0499 Section: PART II - Clinical Research Proposal - Interventions Beuzekom, or Boer. Observations BJA 2008)

Backache/TNS

https://ecap.hss.edu/eCAP/ResourceAdministration/Project/PrintSmartForms?Project=com.webridge.entity.Entity%5BOID%5B7 E7099039664F74FA0FE0FE... 14/36

Patient: If the backache question from LPPSq is negative, then no further questioning. If positive, then the TNS Pre-op, POD 1 and POD

questionnaire will be 6-9

administered. Duration

Research Assistant

will be determined from further follow-up as needed. ([name], Liguori, Zayas. A&A 2005)

Headache/ PDPH

Patient: assess for PDPH, including new incidence of postural Pre-op, 6-9

POD 1 and POD

headache (yes/no), severity (NRS), duration.

Research Assistant

On POD6-9 will only ask about headache and backache.

Incidence of urinary catherization, time until voiding and volume of intake/output

**PACU** 

Medical (yes/no)

record: Incidence

Research Assistant

Blinding assessment PACU Patient Research Assistant

Block assessment Pre-op, PACU Patient Research Assistant

Unexpected adverse events, including ICU admission

Intra-op to POD 1 Medical Record Research Assistant

# Help Help General Methods and Procedures

## 1.0 \* Are controls included in the study? No

1.1 If yes, describe how they will be matched with the study subjects; state whether the controls will have identical data recorded, or describe any differences compared to the intervention subjects.

2.0

#### \* Are all tests Standard of care? No

If not, identify which tests are not standard of care. What source of funds will be used to pay for them (text box below):

The surveys and questionnaires that will be administered by the research staff are not standard of care. The Hospital for Special Surgery Anesthesiology Department Research and Education Fund will be used to pay for them.

- 3.0 \* Will surveys/questionnaires be used? Yes
- 4.0 \* Does the study involve randomization? Yes
- 5.0 \* Does your study included Placebo or No-Treatment Arm? No
- 6.0 \* Does your study included Washout of Previous Medication? No
- 7.0 Data collection sheet should be created for the study and uploaded:

Name Version LMA vs Spinal F&A Data Collection Sheet 120116 0.02 LMA vs Spinal F&A Patient Information Sheet 0.01 LMA vs Spinal F&A REDCap 010417 0.04

#### Help

https://ecap.hss.edu/eCAP/ResourceAdministration/Project/PrintSmartForms?Project=com.webridge.entity.Entity%5BOID%5B7 E7099039664F74FA0FE0FE... 15/36

ID: 2016-0499 Section: PART II - Clinical Research Proposal - Interventions or Observations

# elp Surveys & Questionnaires

1.0 Please add all survey instruments and questionnaires to be used in this

study:

Name

Standard Instument

Upload Instrument Usage of Instrument

View

Headache/PDPH Questionnaire

no

#### Headache/PDPH Questionnaire(0.01)

This instrument will be screen for incidence of puncture headache (PDPH).

used to post-dural

This instrument will be used to View LLPSq yes

LLPSq(0.01)

collect satisfaction with perioperative care.

View

NRS Pain/Nausea/Vomiting

https://ecap.hss.edu/eCAP/ResourceAdministration/Project/PrintSmartForms?Project=com.webridge.entity.Entity%5BOID%5B7 E7099039664F74FA0FE0FE... 16/36

#### NRS Pain and PONV(0.01)

This instrument will be used to assess for pain, nausea, and emesis.

View

no

This instrument will be used to evaluate 3 symptom distress dimensions (frequency, severity, bothersomeness) for 12 symptoms related to opioid used.

View

**ORSDS** Questionnaire

ves

ORSDS Questionnaire(0.01)

**PQRS** Cognitive Domain

PQRS Cognitive Domain(0.01)

This instrument will be used to score cognitive performance.

View

Η

yes

Readiness for This Discharge Questionnaires

instrument will be used to assess if patients are ready to be discharged from the PACU and subsequently, discharged to home.

View TNS Questionnaire yes

Readiness for yes

Discharge Questionnaire(0.01)

TNS Questionnaire(0.01)

This determine neurological instrument if a symptoms patient will be has used (TNS).

transient

to

ID: 2016-0499 Section: PART II - Clinical Research Proposal - Interventions or Observations

# elp Randomization

#### 1.0 Please state who will do the Randomization:

Research staff who are not affiliated with the study will prepare opaque and sealed randomization treatment envelopes.

#### 2.0 Please state when the Randomization will be done:

The randomization will be done before enrollment begins.

### 3.0 Please state how the Randomization will be performed:

Randomizer, an Excel-compatible randomizing program, will be used by non-study research personnel to assign treatments, using two treatment arms and a target enrollment of 18 patients per treatment arm. The non-study research personnel will then prepare opaque sealed treatment envelopes.

#### 4.0 Please state who will insure that the Randomization is carried out and if

#### anyone will be blinded to the Randomization group:

The primary investigator and co-investigators will ensure that randomization is carried out. The research assistants administering surveys/questionnaires and patients will be blinded.

elp ID: 2016-0499 Section: PART II - Clinical Research Proposal - Sample Size & Data Analysis

#### Η

# elp Sample Size and Data Analysis

If you are uncertain about how to calculate your sample size and determine appropriate data analysis, please contact the Epidemiology and Biostatistics Core at [contact] for assistance in completing this section.

1.0

Is this is a case series based only on the patients available using descriptive statistics in lieu of a sample size calculation?

\* No

# Help Help Sample Size and Data Analysis

Support estimates with evidence from the literature of prior studies and perform an appropriate sample size calculation.

For hypothesis testing (e.g., the calculation of p-values using statistical tests), you need to estimate your available sample size and calculate the effect size that will be detectable

https://ecap.hss.edu/eCAP/ResourceAdministration/Project/PrintSmartForms?Project=com.webridge.entity.Entity%5BOID%5B7 E7099039664F74FA0FE0FE... 17/36

Н

Н

ID: using 2016-0499 your proposed Section: PART statistical II - Clinical analysis Research plan. Proposal This also - Sample applies Size to & a Data case Analysis series where you plan hypothesis testing.

1.0 If you have consulted with a statistician, please indicate their

name: [name]

2.0 Proposed sample size analysis, include the following:

Student's t-test, ANOVA, chi-square, regression, etc; Alpha level; Beta or power level; Primary outcome variable estimate (mean +/-s.d. for continuous outcome, frequency/percentage for categorical variable); Number of groups being compared (use 1 for paired analysis within the same subjects); Effect size or change expected between groups; Resulting number per group

1. Proposed analysis (e.g., student's t-test, ANOVA, chi-square,

regression, etc.): Two-sample t-test or Wilcoxon rank-sum test 2. Alpha level: 0.05 3. Beta or power level: 80%

4. Primary outcome variable estimate (mean +/- s.d. for continuous

outcome, frequency/percentage for categorical variable): Mean  $\pm$  SD PACU length of stay =  $132 \pm 42$  minutes ([name] – unpublished data) 5. Number of groups being compared (use 1 for paired analysis within

the same subjects): 2 6. Effect size or change expected between groups: 45 minutes (Mulroy

2000) 7. Resulting number per group: 16 8. Total sample size required: 32 + additional 10% to account for attrition =

36

References:

3.0

Data Analysis: describe how the primary outcome will be analyzed and what types of statistical calculations will be used. Do the same for each secondary outcome. Reiterate briefly the main analysis to be done, which groups, which variables, possible confounders. Address how possible confounders will be identified and handled in analysis:

Balance on demographics and baseline characteristics will be assessed by calculating standardized differences (difference in means or proportions divided by the pooled standard deviation). Balance will be assessed using two thresholds: (1) 1.96 x (2/18)

1/2

= 0.653 and (2) 0.2 (Austin 2009).

The primary outcome will be compared between groups using a two-sample t- test or Wilcoxon rank-sum test. Effect size will be presented as difference in

https://ecap.hss.edu/eCAP/ResourceAdministration/Project/PrintSmartForms?Project=com.webridge.entity.Entity%5BOID%5B7 E7099039664F74FA0FE0FE... 18/36

ID: 2016-0499 means Section: or Wilcoxon-Mann-Whitney PART II - Clinical Research odds with Proposal 95% - confidence Sample Size interval.

& Data Analysis Secondary outcomes with a single measurement per patients will be compared between groups using two-sample t-tests or Wilcoxon rank-sum tests for continuous and ordinal variables, respectively, and  $\chi$ 

or Fisher's exact tests, as appropriate, for binary variables.

Secondary outcomes measured multiple times per patient will be analyzed using the generalized estimating equations method with an identity link for continuous variables and logit link for binary variables. Effect sizes will be presented as difference in means, Wilcoxon-Mann-Whitney odds, or risk difference and relative risk with 95% confidence intervals. Analyses of secondary outcomes will be considered exploratory.

The success of blinding of the patient and research assistant will be assessed using the Bang Blinding Index (Bang 2010).

All analyses will abide by the intention-to-treat principle.

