**Population Patients** 

Vulnerable Populations There are no items to display

- 1.1 If Other, please specify:
- 2.0 Inclusion Criteria: list characteristics that potential subjects and

controls need to have. Use a bullet format, if applicable.

18-75 aged patients

ID: 2016-0499 ASA1-3

Section: PART II - Clinical Research Proposal - Recruitment & Enrollment Elective foot and ankle day surgery procedures, lasting between 1 and 3 hours as per surgeon, performed by 3 co-investigator surgeons. planned for combined popliteal and adductor canal block no contraindications for spinal or LMA general anesthesia

3.0

Exclusion Criteria: list characteristics that would cause you to exclude potential subjects and controls.

Justify any age, ethnicity, language, or gender-based exclusion criteria. Use a bullet format, if applicable.

Incapable of providing informed consent, contraindications for regional or LMA anesthesia (anticoagulation, infection at injection site) anticipated difficult airway, BMI>40, anticipated surgical procedure time less than 1 hour or more than 3 hours, Hx of severe PONV ASA >3, peripheral neuropathy affecting the operative extremity pregnant or nursing women, chronic opioid use (daily use of opioids one month prior to surgery/ patients requiring chronic pain interventions) prone position OSA with planned admission overnight to the hospital known allergy/sensitivity to any study medications planned admission after surgery Non-English speaking

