#### Intraop-protocol:

Spinal/Block Group: Ultrasound (US) guided sciatic nerve blocks in the popliteal fossa and adductor canal block with 25 mL and 10 mL, respectively, of 0.25% bupivacaine (plus 2 mg preservative-free (PF) dexamethasone / 30 ml), performed under procedural IV sedation protocol. IV sedation protocol: midazolam, 2-5 mg IV + Glycopyrrolate, 0.1 mg IV + Ketamine, 10-20 mg, + propofol as needed. Spinal protocol: 45-60 mg 1.5% mepivacaine, depending on the expected case duration (45 mg for cases with projected duration 1-2 hours, 60 mg

https://ecap.hss.edu/eCAP/ResourceAdministration/Project/PrintSmartForms?Project=com.webridge.entity.Entity%5BOID%5B7 E7099039664F74FA0FE0FE... 10/36

ID: 2016-0499 for cases with Section: projected PART duration II - Clinical 2-3 hours). Research Intraoperative Proposal - sedation Interventions maintained or Observations with propofol infusion and

ketamine, 10 mg/hr (in addition to the 10-20 mg given for block sedation).

General Anesthesia/Block Group. Blocks performed as above. General anesthesia protocol: After induction with propofol and insertion of the LMA, anesthesia maintained with titrated propofol infusion, sevoflurane, ketamine 10 mg/hr (in addition to the 10-20 mg given for block sedation).

Both groups will receive IV ondansetron (4 mg), famotidine (20 mg), dexamethasone (4 mg in addition to block dexamethasone) and ketorolac 30 mg (unless age>75 or weight<60 kg, then 15 mg).

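### Should projected case duration be a randomization stratum or a term in the primary analysis?

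*Combined protocol and SAP*

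**What the plan says.** - **Primary analysis** (Sample Size and Data Analysis, item 3.0): "The primary outcome will be compared between groups using a two-sample t- test or Wilcoxon rank-sum test". No covariate is named. The form's own prompt for this item reads "Address how possible confounders will be identified and handled in analysis".
- **Baseline balance** (same item): standardized differences are calculated. "Balance will be assessed using two thresholds: (1) 1.96 x (2/18" begins a formula, broken across lines, that comes to 0.653; the second threshold is 0.2. No action is attached to either.
- **Allocation** (Randomization, items 2.0 and 3.0): "The randomization will be done before enrollment begins", "using two treatment arms and a target enrollment of 18 patients per treatment arm", in opaque sealed envelopes. No stratum or block size is named.
- **Projected duration**: an eligibility item (Inclusion Criteria: "lasting between 1 and 3 hours as per surgeon"), checked by the research assistant beforehand (Study-Specific Procedures: "Identify eligible patients on schedule day before surgery. Confirm length of surgery"), and used to choose between two spinal dose bands (Intraop-protocol: "45 mg for cases with projected duration 1-2 hours, 60 mg" for the longer cases). The dose bands themselves are not at issue here.

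**The concern.** The protocol already splits patients at 2 hours on a factor known before the envelope is opened. It also says that waiting for the spinal to resolve can delay discharge (Assessment of Research Procedures, item 1.0), and discharge readiness is the primary outcome. With 36 patients, a noticeable imbalance in long cases between arms is quite likely. The form asks how confounders will be handled, and the answer is a balance check with no consequence followed by an unadjusted test. If duration predicts PACU time, chance imbalance could move the estimate, and precision that might have been gained by adjustment would be lost. The chance to stratify ends once the envelopes are made.

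**Working it through.** **Inputs from the plan.** Difference 45 min, SD 42 min, alpha 0.05 (taken as two-sided), power 80%, 16 per group, 36 in total. The share of outcome variance explained by projected duration (R²) and the number of long cases are not given. Both are assumed below and shown as ranges.

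**1. The plan's own figure.** With d = 45/42 = 1.071, the noncentral t gives 80.9% power at 15 per group and 83.5% at 16. Dividing 15 by the Wilcoxon efficiency 3/π gives 15.7, hence 16. Simulated Wilcoxon power at 16 is about 81%. The stated size reproduces and meets its target with either test.

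**2. How likely is imbalance?** Under 18:18 allocation of 36 patients, K of them long (hypergeometric), the chance that the arms differ by at least 4 long cases is 29-32% for K = 12, 14, 16 or 18 and 16-18% for K = 13, 15 or 17. If half are long, the standardized difference exceeds 0.2 in about 74% of allocations (a 10 vs 8 split already gives 0.22) and 0.653 in about 9%.

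**3. What would it do to the estimate?** With half the cases long, the long-minus-short difference implied by R² is 2 × 42 × √R². A 4-case imbalance (11 vs 7) shifts the unadjusted difference by 4/18 of this if duration acts in both arms. If it acts only in the spinal arm, that arm's mix is off by 2/18, so the shift is half as large.

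| Assumed R² | Long minus short (min) | Shift, both arms (min) | Shift, spinal arm only (min) |
|---|---|---|---|
| 2% | 11.9 | 2.6 | 1.3 |
| 5% | 18.8 | 4.2 | 2.1 |
| 10% | 26.6 | 5.9 | 3.0 |
| 20% | 37.6 | 8.3 | 4.2 |

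For scale, readiness is assessed every 15 minutes, and the unadjusted 95% CI half-width at 16 per arm is 2.04 × 42 × √(2/16) ≈ 30 min. Chance imbalance of this kind is already part of the sampling variation that the interval covers.

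**4. Power of stratified allocation plus ANCOVA, equal effect in both arms.** Using d/√(1−R²) with 29 df: 83.4%, 84.1%, 85.2%, 87.0% and 90.6% for R² of 0, 2, 5, 10 and 20%, against 83.5% as planned.

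**5. Power if duration acts only in the spinal arm.** In simulations at 16 per arm with half the cases long, an effect of 26.6 or 37.6 min takes power from 85.4% to 86.5% or from 87.4% to 89.5%. A rerun holding the SD at 42 in each arm (40,000 runs) gives 83.7% to 84.3% and 84.0% to 85.7%; for 18.8 min there is essentially no gain (83.6% to 83.8%).

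**6. Each change alone.**
- Stratifying but keeping the t-test makes the test conservative: type I error about 0.029 to 0.044 for R² from 20% down to 5% (both arms).
- Adjusting without stratifying costs about 1.5 power points if R² = 0. It still loses roughly half a point to one point for a 19-27 min effect confined to the spinal arm.

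**7. Predictability.** In a permuted block of 4, the last assignment is always determined, and the third is determined when the first two match (probability 1/3). So (1 + 1/3)/4 = 33% are determined for someone tracking assignments, and 30-33% once unfinished blocks are counted. In a single 18:18 list (assumed), the expected determined run at the end is 2 × 18/19 = 1.9 patients, and 1.9/36 = 5%.

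**The case for a change.** The strongest case for acting is that the pair of changes has almost no statistical downside: 0.1 power point if duration explains nothing, and 3.5 to 7.1 points gained if it explains 10% to 20% of variance in both arms. Imbalance in a trial this small is likely, the factor is in hand before allocation, and the cost is a second envelope set, one data field and a few sentences. Naming a covariate in advance would also answer the form's prompt more directly.

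The facts stand, and if duration were known to be strongly prognostic in both arms the argument would be good. Several parts do not carry over to this trial:

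- **No evidence of prognosis.** The passages on delayed discharge concern the spinal itself, which is the treatment contrast, not projected duration. The protocol scales the spinal dose to expected duration and says the amount will be chosen to avoid prolonged numbness (Greater Than Minimal Risk, item 1.0). The outcome clock starts at PACU admission, after the longer operation is over. Duration may explain little.
- **A cost beyond envelopes.** Anesthesiologist or surgeon co-investigators obtain consent (Consent Information, item 1.0), and only patients and research assistants are listed as blinded (Randomization, item 4.0). At one site with three surgeons, small fixed blocks within strata weaken concealment. Undisclosed varying block sizes would lessen this but not remove it. The arms could also depart from 18:18, at worst 20:16 with blocks of 4.
- **The stratum is not ready to use.** A case projected at exactly 2 hours falls in both bands.
- **The balance check opens no loophole.** The primary test is already specified as unadjusted, so the standardized differences are descriptive. A rule against choosing covariates from them would change nothing.

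**Conclusion.** The concern describes the plan correctly but does not show a defect. Randomization makes the unadjusted comparison valid, the sample size reproduces, and power is above its target. Stratifying and adjusting together would gain about 0 to 2 power points under the one mechanism the documents suggest, and would prevent shifts of about 1 to 4 minutes from a 4-case imbalance against a 45-minute target. In return it gives up 1 degree of freedom, possibly the exact 18:18 split, and some unpredictability of allocation; either change made alone can do harm. The more favorable figures need an R² of 10% to 20% acting in both arms, which nothing in the documents supports or excludes. All these sizes assume an SD of 42 minutes and, for the shifts and simulations, that half the cases are long. Experienced statisticians could reasonably choose either design, so the plan can stand as written on this point.

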# elp Target Enrollment

- 1.0 \* What is the maximum number of subject you plan to enroll in this study at HSS?(Please enter a number) 36
- 2.0 If this is a multi-center study, indicate the projected total subject accrual across all sites.

Н

Н

elp ID: 2016-0499 Section: PART II - Clinical Research Proposal - Interventions or Observations

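### GEE for repeated secondary outcomes names no variance estimator or reference distribution; with 16 to 18 patients per arm, the usual default gives continuous-outcome intervals 6% to 7% too narrow

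*Combined protocol and SAP*

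**What the plan says.** Sample Size and Data Analysis, item 3.0, states: "Secondary outcomes measured multiple times per patient will be analyzed using the generalized estimating equations method". The specification in full is the "generalized estimating equations method with an identity link for continuous variables and logit link for binary variables". Effects are to be given as differences in means, Wilcoxon-Mann-Whitney odds, or "risk difference and relative risk with 95% confidence intervals". The same item adds: "Analyses of secondary outcomes will be considered exploratory". It does not mention a robust or model-based variance, a working correlation, the terms in the model, a small-sample correction, or the distribution behind the intervals.

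The number of independent units is small. The Randomization section describes assignment "using two treatment arms and a target enrollment of 18 patients per treatment arm". Item 2.0 of the sample size section gives a total of "32 + additional 10% to account for attrition", which it rounds to 36.

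The Data Collection table lists pain, nausea and vomiting, the cognitive domain, and discomfort and needs before surgery, at 1 and 2 hours in the PACU, and on the first postoperative day. That is four time points, three of them postoperative.

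**The concern.** In GEE the patient is the cluster. The sandwich variance and its normal or chi-square reference are justified when clusters are many; with 32 to 36 they are only approximate. The uncorrected sandwich is biased downward, and the normal reference ignores the uncertainty in the variance estimate. Both errors make intervals for continuous outcomes too short.

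These outcomes supply most of the evidence for the second research question, on pain, nausea, discomfort and opioid use. Many are compared without multiplicity control, so intervals that are too short add to the chance findings that a reader will notice. The plan also uses t-tests for continuous outcomes measured once, so within one trial the repeated outcomes could be handled less carefully than the single ones.

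**Working it through.** **Inputs.** Patients per arm k = 18 (Randomization, item 3.0) or 16 (sample size, item 2.0). Nominal level 5% two-sided, from the 95% intervals. Three postoperative time points (Data Collection table). Assumed, not in the documents: normal outcomes, complete data, equal arms, and the uncorrected sandwich with a normal or chi-square reference.

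**The plan's own figure.** The documents state no error rate for the GEE analyses, so the figure to reproduce is the sample size, which fixes k. With a difference of 45 and SD of 42 minutes, the normal approximation gives 2 × (1.960 + 0.842)² × 42² / 45² = 13.7, so 14 per group. The exact t calculation needs 15 (80.8% power). Dividing by the Wilcoxon efficiency, 15 / 0.955 = 15.7, gives the stated 16. Then 32 × 1.10 = 35.2, rounded up to 36. The figures reproduce.

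**Single contrast, identity link.** With balanced complete data, the uncorrected sandwich variance of an arm difference (at one time point, or averaged over time) equals (k − 1)/k times the unbiased variance. The z test therefore rejects when |t| on 2k − 2 df exceeds 1.960 × √((k − 1)/k).

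| k per arm | df | effective cut-off | correct t cut-off | width ratio | type I error | coverage |
|---|---|---|---|---|---|---|
| 18 | 34 | 1.960 × √(17/18) = 1.905 | 2.032 | 0.937 | 6.5% | 93.5% |
| 16 | 30 | 1.960 × √(15/16) = 1.898 | 2.042 | 0.929 | 6.7% | 93.3% |

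No within-patient correlation has to be assumed for these figures.

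**Tests with several degrees of freedom (not in the plan).** If a test on q df were added, the uncorrected Wald statistic is k/(k − 1) times Hotelling's T². Its true size is P(F(q, 2k − 1 − q) > χ²(q, 0.95) × ((k − 1)/k) × (2k − 1 − q) / (q(2k − 2))).

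- Group-by-time over three postoperative points, q = 2: k = 18 gives P(F(2, 33) > 2.746) = 7.9%; k = 16 gives P(F(2, 29) > 2.715) = 8.3%.
- Joint arm test over the same points, q = 3: k = 18 gives P(F(3, 32) > 2.315) = 9.4%; k = 16 gives P(F(3, 28) > 2.279) = 10.1%.

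**Effect of correcting.** In this balanced case the Kauermann-Carroll variance is unbiased.

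- Single contrast, t on 2k − 2 df: 5.0%. Corrected variance but still a normal reference: 5.8% (k = 18) and 5.9% (k = 16), so both parts are needed.
- Several df, F on patients minus 2: 5.5% for q = 2, 6.1% to 6.3% for q = 3, 7.0% to 7.3% for q = 4. This reference is not enough for joint tests. Hotelling's own F, on q and 2k − 1 − q df, is exact here.

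**Binary outcomes, logit link.** Simulation with assumed within-patient correlation 0.5, event rates 0.15, 0.30 and 0.50, and 1,200 runs per scenario (Monte Carlo standard error about 0.6 to 1 percentage point). The uncorrected test of the overall group effect had size 4.5% to 7.6%. Joint and interaction tests had 4.4% to 7.9% at rates 0.30 to 0.50 and 1.2% to 3.8% at 0.15, where 25% to 44% of the fits with group-by-time terms gave no usable estimate. With the correction and a t or F reference, sizes were 0.4% to 5.1%.

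**Fewer patients at 2 hours.** The schedule makes this assessment depend on the patient not yet being ready for discharge. The documents give no number who would remain. With 8, 6 or 5 per arm assumed, the single-contrast formula gives 8.8%, 10.4% or 11.8%.

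**The case against.** The strongest reply is that the plan does not specify robust errors at all. This is an application form, a statistician was consulted, and a correction may be intended. That stands: the figures describe what follows if the customary default is used, not a method the plan has chosen. It does not remove the point, because nothing in the text excludes that default.

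The second reply is that the analyses are exploratory and the primary comparison is a t-test or Wilcoxon test. This also stands and keeps the point minor. The label does not, however, turn an interval with 93.5% coverage into a 95% interval.

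A reader might infer something stronger: false-positive rates of about 12% for the repeated secondary outcomes. The documents do not support that. The same formula with q = 4 does give 11.3% to 12.3%, but it needs a joint test over all four time points. The plan proposes no such test, and it would count the preoperative value as part of the treatment effect. The 11.8% for a 2-hour contrast rests on an assumed 5 patients per arm. Nor can the inflation be extended to every repeated outcome: for binary outcomes it is small, and with rare events the problem is conservatism and models that cannot be fitted.

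**Conclusion.** The point holds as a minor one. The plan leaves open the part of GEE that matters most with 32 to 36 clusters. Under the customary default, a continuous between-group difference would carry an interval about 6% to 7% too narrow, with coverage of 93.5% to 93.3% and type I error of 6.5% to 6.7%. If tests with several degrees of freedom over the postoperative points were added, the error would be about 8% for group-by-time and 9% to 10% for a joint arm test.

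The result is exact only for normal outcomes, balanced arms and complete data; bounded or skewed scores such as pain ratings and missing assessments would shift it. Conclusions on time to discharge readiness are not affected.

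**What to change.** Add to item 3.0 that continuous repeated outcomes are analysed by GEE with a bias-corrected sandwich variance (for example Kauermann-Carroll) and a t reference on patients minus 2 degrees of freedom. A mixed model for repeated measures with Kenward-Roger degrees of freedom would serve equally well. State the working correlation, the model terms, and whether the reported effect is an average over time or a contrast at each time point.

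If a test with several degrees of freedom is wanted, name it and give it a Hotelling-type or Kenward-Roger F reference; F on patients minus 2 with the Kauermann-Carroll variance is not sufficient. For binary outcomes, say what will be reported if a model with group-by-time terms cannot be fitted.

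The cost is a few lines of text and a software option, settled before the data are analysed. No patients, visits or data items change. The only downside is slightly wider intervals for continuous outcomes: 1/0.937 = 1.07 to 1/0.929 = 1.08 times the uncorrected width.
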